3.1 Number of Subjects

We will recruit 610 participants total. 600 recruited participants will be smokers enrolled from any of our recruitment methods outlined in "Patient Participant Recruitment" below. Half of the enrolled participants (300 smokers) will receive the intervention immediately after consent, and the other 300 will receive the intervention after 6 months. Additionally, we will recruit 10 staff participants: 5 staff from Bellevue Hospital and 5 staff from NYU Lutheran.

3.2 Gender of Subjects

There are no enrollment restrictions based on gender.

3.3 Age of Subjects

Age ≥18 years

3.4 Racial and Ethnic Origin

There are no enrollment restrictions based on racial or ethnic origin.

3.5 Eligibility Criteria

3.5.1 Patient participants:

- 1) age ≥ 18 years
- 2) Has smoked a cigarette in the past 30 days, even a puff
- 3) Interested in receiving smoking and financial counseling
- 4) Self-reported income below 200% of the current federal poverty level for a given household composition
- 5) New York City resident
- 6) English or Spanish language
- 7) Able to provide informed consent, and
- 8) Does not have a representative who manages his/her funds (to ensure the participant has the ability to manage household money). We will exclude participants who report being pregnant or breastfeeding (unable to receive NRT).

3.5.2 Hospital staff participants:

- 1) Must be current medical or non-medical provider or administrator at Bellevue Hospital or NYU Lutheran Medical Center

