2.2 Aims

1. Estimate the acceptability of the integrated program and its effect on participants' disposable income, savings, financial stress, mental wellness, and abstinence from cigarettes.
2. Estimate the per-patient cost of the integrated program.
3. Identify barriers and facilitators toward wide-scale implementation of the program model.

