Third, at the Bellevue site, we will receive referrals from the hospital's regular smoking cessation program. The smoking cessation program will let patients know about the study and give them the study flyer (Appendix A). The program will ask if they are interested in being referred to our study to learn more about the study. For patients who give permission to be referred, the Bellevue smoking cessation program will send our study team an NYUMC encrypted email with the name and preferred contact information. To all referred patients, a study RA will send a letter (Appendix B) and the recruitment flyer (Appendix A). Two weeks after mailing the materials, an RA will call the patients to discuss the study, screen interested patients for eligibility, and schedule eligible participants for an appointment to complete an IRB-approved informed consent process. All identifiable screener data for patients who are deemed ineligible or who do not wish to participate in the study will be destroyed. We will only keep itemized screener data to report to the funding agency, though no PHI will be saved and we will only label participants with a pre-screening number.

Fourth, we will work with medical center IT to set up a consult in EPIC that allows physicians to refer Lutheran patients to the program. Providers will be given an overview of the study and eligibility criteria prior to implementing the EPIC consult, so that they may filter some of the referrals received. If a patient is deemed eligible for referral, physicians will inform their patients that someone from the study team will contact them within the next two weeks to screen for study eligibility. Providers will also have copies of our study flyer (Appendix A) to hand out to patients who are interested, so the patient may also reach out directly to the research coordinator as directed by the flyer. Each day, a study team member will check EPIC for a list of patients referred by their providers. An RA will contact the patients to screen for eligibility. Those who are eligible will be scheduled for a consent appointment. Patients who are ineligible to participate in the study will be referred to the NY State Quitline. All identifiable screener data for patients who are deemed ineligible or who do not wish to participate in the study will be destroyed. We will only keep itemized screener data to report to the funding agency, though no

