4.4 Patient Participant Baseline Interview

After obtaining informed consent, a RA will administer a baseline survey (Appendix D) assessing sociodemographics, tobacco use, motivations and readiness to quit, income, financial stress, mood, household spending patterns and other intervention covariates or mechanisms.

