4.6.4 Both Arms: Patient Participant Follow-up Surveys

We will conduct a telephone follow-up survey 6 months (Appendix F) and 12 months (Appendix G) after enrollment with all participants. A study team member will make 10 attempts over 4 weeks to complete the survey (Appendix J). We will mail a hard copy or email the survey if participants do not want to complete the survey over the phone. The surveys will re-assess participant behavior and characteristic assessed at baseline, and a short series of close-ended and open-ended questions about satisfaction with the interventions. The first 150 participants will complete an additional 2 month follow up survey (Appendix E) in order to obtain preliminary data. After the first 150 enrollments, the 2 month survey will be retired and the remainder of the 450 enrollments will only complete surveys at baseline, 6 months and 12 months. All enrollees that signed a consent form indicating the additional 2 month survey will be eligible to participate in that survey and will be compensated accordingly. Participants will be paid \$15 as reimbursement for their time completing the surveys. The additional follow-up survey (Appendix S) to gain feedback from participants who are NYCHA-residents on their smoking cessation needs will be conducted via phone. Patients being contacted are already enrolled in the study.

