5.1 Data Analysis

To evaluate the acceptability and feasibility of the integrated intervention, we will calculate the number of counseling sessions completed and satisfaction with treatment, which we will summarize descriptively using count and frequency statistics. We will calculate additional measures of study feasibility and acceptability, including the eligibility rate among people screened, enrollment rate among those eligible, reasons for ineligibility or refusal, and the proportion of participants who would recommend the intervention to other smokers. To estimate the effect of the integrated intervention on outcomes we will use generalized estimating equations (GEE) to model the main effects of time (baseline to 6 and 12 months)

and treatment group, and the interaction of time and treatment, on each outcome. GEE will allow us to determine whether intervention effects are present and whether they change over time.

We will also calculate and sum all time and costs of administering the interventions. Each intervention staff member will record their activity in a web-based intervention tracking system (using REDCap). Staff prospectively input detailed information for a 1-week sample of their activities and associated time required on a monthly basis. Those recording their time and activities have flexibility to add or tailor their entry form to match their exact activities. We will assign a dollar value for each unit of staff time based on the wage and fringe rate of those who perform the activity using regional labor rates from the US Bureau of Labor Statistics. We will also keep track of medications ordered and used by participants, which we will assign a dollar value to using Red Book, a wholesale pharmaceutical pricing index. Once all costs are compiled and summed, they will be adjusted to constant dollars using the medical care component of the Consumer Price Index.

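### One-puff entry can mix daily, intermittent and just-quit smokers, but the abstinence model in section 5.1 makes no use of baseline smoking frequency

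*Combined protocol and SAP*

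**What the plan says.** Entry (3.5.1) requires that the person "Has smoked a cigarette in the past 30 days, even a puff" and is "Interested in receiving smoking and financial counseling". No minimum number of smoking days or cigarettes is set. One recruitment route (4.2) takes referrals from Bellevue's "regular smoking cessation program".

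The first aim (2.2) includes estimating the effect on "financial stress, mental wellness, and abstinence from cigarettes". Neither the follow-up section (4.6.4) nor the analysis section (5.1) says over what period a participant must not have smoked to count as abstinent. Follow-up is described as "We will conduct a telephone follow-up survey 6 months (Appendix F) and 12 months (Appendix G) after enrollment with all participants", and "The surveys will re-assess participant behavior and characteristic assessed at baseline". The survey instruments are in appendices that were not available for this review.

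The baseline survey (4.4) covers "tobacco use, motivations and readiness to quit", among other items. Under 4.5 the participant is randomized when that survey ends, so its answers precede assignment. Randomization is 300 per arm, stratified by site only (2.3).

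The effect analysis in 5.1 is a GEE for each outcome. Its terms are time (baseline and both later surveys), treatment group and their interaction. It names no covariates and no link function.

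**The concern.** Any abstinence window shorter than 30 days fits inside the entry window. A person who smokes on a few days a month can then be eligible as a smoker, already abstinent by that window at randomization, and abstinent again at month 6 with no change in behavior. A daily smoker cannot. Baseline smoking frequency may therefore be one of the strongest predictors of the outcome, and the model leaves it out.

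At stake is the month-6 contrast, the last comparison before the control arm is offered counseling (4.6.2). Unchanged intermittent smokers raise the abstinence rate in both arms by nearly the same amount. This pulls the risk ratio toward 1, slightly shrinks the risk difference and adds variance that a covariate measured before randomization could partly remove.

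**Working it through.** **The plan's own figure.** The protocol states 600 patients, 300 per arm. It gives no alpha, power, quit rates or dropout, so this figure cannot be reproduced, and no stated power exists to compare against. Every rate below is an assumption.

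**Step 1: how often unchanged intermittent smokers look abstinent.** If smoking days follow a Poisson process with λ days per 30, the chance of none in 7 days is exp(−7λ/30), and of none in 30 days exp(−λ):

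| λ | none in 7 days | none in 30 days |
|---|---|---|
| 1 | 79% | 37% |
| 2 | 63% | 14% |
| 4 | 39% | 2% |
| 8 | 15% | <0.1% |

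A simulation was also run with 200,000 non-daily smokers per scenario. Individual daily smoking probabilities were beta distributed (precision 4; mean 4/30, 8/30 or 12/30), day-to-day correlation was 0 or 0.5, and entry required at least one smoking day in 30. With no behavior change:

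- no smoking in the last 7 days at baseline: 11–44%;
- no smoking in the last 7 days at month 6: 12–50%;
- no smoking in the last 30 days at month 6: 1.2–18.4%.

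A 30-day window therefore reduces the problem but does not remove it.

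**Step 2: effect on the contrast.** Let f be the non-daily share, q the proportion of non-daily non-quitters who look abstinent, and p the true quit rate. The observed rate is p + f(1 − p)q, so the risk difference is multiplied by (1 − fq).

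Assume p = 5% (control) and 12% (intervention), f = 20%, q = 35%:

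- Control: 0.05 + 0.2 × 0.95 × 0.35 = 0.1165.
- Intervention: 0.12 + 0.2 × 0.88 × 0.35 = 0.1816.
- Risk difference: 0.07 × (1 − 0.07) = 0.0651.
- Risk ratio: 1.56, against 2.40 undiluted.

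**Step 3: precision.** This uses a two-sided 5% Wald test, 300 per arm with no dropout, and standard error √(V/300).

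- Undiluted: V = 0.05 × 0.95 + 0.12 × 0.88 = 0.1531; power 87%.
- Diluted, unadjusted: V = 0.1165 × 0.8835 + 0.1816 × 0.8184 = 0.2516; standard error 0.0290; power 61%.
- Diluted, stratified by daily/non-daily: rates in the non-daily stratum are 0.3825 and 0.4280, so V = 0.8 × 0.1531 + 0.2 × (0.3825 × 0.6175 + 0.4280 × 0.5720) = 0.2187. This is 13% lower; power 67%.

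The same formulas across the assumed range:

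| f | q | observed rates | risk difference (points) | variance saved | power, unadjusted → adjusted |
|---|---|---|---|---|---|
| 10% | 12% | 6.1% v 13.1% | 6.92 | 1.3% | 82% → 83% |
| 20% | 12% | 7.3% v 14.1% | 6.83 | 2.0% | 78% → 79% |
| 20% | 35% | 11.7% v 18.2% | 6.51 | 13.1% | 61% → 67% |
| 20% | 50% | 14.5% v 20.8% | 6.30 | 23.2% | 53% → 64% |
| 30% | 50% | 19.3% v 25.2% | 5.95 | 25.6% | 42% → 53% |

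**Step 4: a harsher model.** Suppose treatment does nothing for a share f, who are abstinent at rate q in both arms. Rates become (1 − f)p + fq. With 10% v 18% among the others, f = 10% and q = 60%, the rates are 15.0% v 22.2%. The difference falls from 8.0 to 7.2 points and power from 81% to 62%.

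**Step 5: the baseline row.** If abstinence is defined over 30 days, almost everyone is non-abstinent at baseline because that is how they qualified. With a logit link (usual for a binary outcome, but not stated), the baseline log-odds run toward minus infinity. The time and interaction terms measured from baseline then cannot be estimated, or only very unstably. The model needs changing for abstinence whichever window is chosen.

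**The case against.** The strongest objection is that the size is unknown. The illustration uses mid-range inputs; at low-end values unadjusted power is 78–82%, and the risk difference moves little even in the illustrated case. The protocol describes a pilot that estimates effects, states no power and names several outcomes beside abstinence. Broad entry is a legitimate choice. All of this stands, and it limits the point to efficiency and interpretation.

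It can also be said that the planned model already contains baseline. That lets a chance imbalance in baseline abstinence show, but it does not use smoking frequency to explain variation at month 6.

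A reader might infer more in four places, and the documents do not support it:

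- **That defining abstinence over 30 days ensures nobody is abstinent at baseline.** On the telephone routes (4.2), screening precedes the consent visit and baseline survey, and no re-screening is described. A person whose last puff was 28 days before the call could be past 30 days at baseline. A 30-day window also misses people who quit in the final month, so the choice of window is a trade-off.
- **That the absence of biochemical confirmation adds to this problem.** An intermittent smoker with no cigarette in 7 days answers truthfully. Confirmation is a separate question.
- **That cessation-program referrals bring in many recent quitters.** The call comes two weeks after mailing, so someone who had stopped three weeks before referral would be about five weeks out and ineligible. Someone who stopped around referral would still qualify, but this route is at Bellevue only and its yield is not given.
- **That no window exists.** The unseen survey appendices may contain a timed question. It would still need to be named in 5.1 as the outcome definition.

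**Conclusion.** The concern holds as a missed adjustment. Entry permits wide variation in baseline smoking, the relevant measure is taken before randomization, and the abstinence model does not use it. Randomization makes the extra apparent abstainers comparable between arms, so there is no bias by arm and no added risk of a false positive from this source.

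Under the assumed ranges (10–30% non-daily; 12–50% of unchanged non-daily smokers abstinent over 7 days), 1.2 to 15 percentage points of the sample would look abstinent with no treatment effect (0.10 × 0.12 to 0.30 × 0.50). Adjustment saves about 1% to 26% of the variance. It recovers only part of the lost power: 6 of 26 points in the illustrated case. If few entrants are non-daily, the matter is negligible.

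**What to change.** In section 5.1:

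1. Add baseline smoking frequency (daily versus non-daily, or days smoked in the past 30) as a covariate in the abstinence model. Report the standardized risk difference as well as any odds ratio, since the variance savings above refer to the risk difference.
2. Fit that model to the 6- and 12-month outcomes only, with the 6-month contrast named as the randomized comparison. Do not treat baseline abstinence as an outcome row.
3. State the abstinence window. If it is shorter than 30 days, add a sensitivity analysis limited to participants who did not already meet it at the baseline survey. This restriction uses pre-randomization data, so the comparison remains randomized.

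The cost is analysis-plan wording and, if the baseline instrument does not already record smoking days, one survey item. No extra patients or visits are needed. The sensitivity analysis uses somewhat fewer participants: with a 7-day window and the assumptions above, about 7 to 79 of 600 would be left out (600 × 0.10 × 0.11 to 600 × 0.30 × 0.44).

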Second, the counselor will initiate money management counseling. [name], a collaborator on the project, will train all study counselors in financial counseling prior to the first counseling sessions. [name] will not have access to PHI, but will act as a consultant to the study team regarding any issues that pertain to the financial counseling aspect of the study. Participants will first describe their longer-term goals, and based on these longer-term goals, will be encouraged to set shorter-term financial goals for their money management. Next, participants will, assisted by a timeline follow-back calendar, complete an inventory describing their sources of income, expenditures (both monetary and in-kind), debts and asset balances. Based on this inventory, participants will be asked to make a budget based on smoking cessation at the time of their future quit date. This budget will list planned expenditures, with those made possible by smoking cessation highlighted and listed separately to increase their saliency and reward value.

Lastly, the counselor will complete a tobacco use intake and brief counseling (Appendix H) with the participant. Topics covered will include: 1) Assessment of smoking and quitting history, 2) Assessment of current readiness to quit through ratings of “importance” and “confidence”, 3) Strategies to raise importance and confidence ratings, 4) Preparations for quitting, 5) Identification of top barriers toward quitting and smoking triggers, as well as coping strategies to address each trigger, 6) NRT use and barriers to use, and 7) Setting a quit date in the next 30 days. Participants will receive a flyer (Appendix Q) on how to use NRT and its possible risks and side effects.

Session 2 (See Appendix H, p. 17): Session 2 will be completed in-person and will begin with follow-up on the prior session’s financial counseling to assess short-term goals (e.g., enroll in benefits) and challenges, and then will transition to focus on smoking cessation. Topics covered will again include: 1) Assessment of smoking and quitting history, 2) Assessment of current readiness to quit through ratings of “importance” and “confidence”, 3) Strategies to raise importance and confidence ratings, 4) Preparations for quitting, 5) Identification of top barriers toward quitting and smoking triggers, as well as coping

strategies to address each trigger, 6) NRT use and barriers to use, and 7) Setting a quit date in the next 30 days.

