4.6.2 Control Arm: Waitlisted Integrated Smoking Cessation and Financial Counseling

Six months after enrolling, participants randomized to the Control Group will receive all of the services described in the Intervention Group section above. Starting 3 weeks before their 6-month time point, study staff will call patients to schedule a counseling appointment (Appendix I). Patients in the control arm will not receive any procedures or counseling in the first six months.

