4.6.3 Both Arms: Nicotine Replacement Therapy (NRT)

Participants in both arms will be eligible to receive a free four-week supply of NRT. Following the US Public Health Service guidelines for the treatment of persons who smoke ≥ 10 cigarettes per day, participants will receive combination NRT (patch plus gum or patch plus lozenge, depending on patient preference).⁵⁰ As we have done on other studies, we will order participants' NRT from drugstore.com after obtaining the participants' NRT preference during counseling. Drugstore.com will mail the NRT to our study office before the first counseling session. Counselors will provide the NRT and review proper use during the first session.

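### Waitlist controls are given NRT about six months after their pregnancy/breastfeeding screen, and the protocol text states no re-check before supply

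*Combined protocol and SAP*

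**What the plan says.** Section 3.5.1 (Patient participants) closes its list with an exclusion and its reason: "We will exclude participants who report being pregnant or breastfeeding (unable to receive NRT". The criterion is self-reported and is applied at screening, which under Section 4.2 comes before consent.

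For the control arm, Section 4.6.2 states: "Six months after enrolling, participants randomized to the Control Group will receive all of the services described" for the Intervention Arm. Until then, "Patients in the control arm will not receive any procedures or counseling in the first six months". The contact that leads into treatment is a telephone call: "Starting 3 weeks before their 6-month time point, study staff will call patients to schedule a counseling appointment (Appendix I").

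Section 4.6.3 makes a free four-week NRT supply available to both arms. On logistics it says "Drugstore.com will mail the NRT to our study office before the first counseling session", and then "Counselors will provide the NRT and review proper use during the first session". Section 4.6.1 adds, for session 1, a discussion of NRT use and barriers, and written information: "Participants will receive a flyer (Appendix Q) on how to use NRT and its possible risks and side effects".

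**The concern.** The reason given for the exclusion is about receiving the drug, so the answer matters on the day the drug is supplied. In the Intervention Arm the two moments are close together, because counseling starts immediately after enrollment. In the Waitlist Arm they are about half a year apart, and pregnancy and breastfeeding status can change in that time. The protocol wants the safeguard, but for one of its two arms the text rests it on an old answer.

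What is at stake is participant safety and adherence to the protocol's own criterion. Nothing statistical depends on it.

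**Working it through.** There is no figure in the plan to reproduce. The check is a reading of every stated contact with a control participant up to NRT handover, followed by simple arithmetic on timing and scale.

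**Timing.** Six months is about 26 weeks. The scheduling calls begin three weeks earlier, at about week 26 − 3 = 23. At handover the screening answer is therefore at least about 26 weeks old. It is older for anyone screened by telephone and given a later consent appointment.

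**Stated steps that might refresh the answer.**

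| Step | Section | What the text says it does | Stated to ask about pregnancy or breastfeeding? |
|---|---|---|---|
| Baseline survey | 4.4 | "assessing sociodemographics, tobacco use, motivations and readiness to quit, income, financial stress, mood, household spending patterns and other intervention covariates or mechanisms" | Not named |
| 2-month survey | 4.6.4 | Preliminary data, first 150 enrollees only | No; also about 6 − 2 = 4 months before supply |
| Scheduling call | 4.6.2 | Books the counseling appointment | No |
| 6-month survey | 4.6.4 | Re-assesses what was measured at baseline | Not named; 10 attempts over 4 weeks, so it may follow session 1 |
| NRT preference | 4.6.3 | Patch plus gum, or patch plus lozenge | No |
| Session 1 | 4.6.1, 4.6.3 | NRT use and barriers, risk flyer, handover | No |
| Weekly meetings of the principal investigator and counselors | 5.2 | Treatment fidelity, review of active patients | No |
| Medical record review | 4.6.5 | Health care utilization, contact details | No |
| Risks and protections | 6.1, 6.2 | Withdrawal, confidentiality, distress, adverse event reporting | No |

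Pregnancy and breastfeeding are mentioned as participant conditions only in Section 3.5.1. The 6-month survey is the nearest candidate, but it repeats baseline content that does not name either condition, and no section makes it a condition for supplying NRT.

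**Scale.** The number of controls is 300 (Section 3.1). Let *p* be the share who are pregnant or breastfeeding at session 1 and accept NRT. The documents give no sex or age mix, session-1 attendance or NRT uptake, so *p* is an assumption:

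- *p* = 0.1%: 300 × 0.001 = 0.3 people
- *p* = 1%: 300 × 0.01 = 3 people
- One expected person: *p* = 1/300 = 0.33%

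**The case against.** The strongest reply is that the protocol body is not the whole plan. The screener (Appendix C), the 6-month survey (F), the counseling guide (H), the scheduling script (I), the NRT flyer (Q) and the consent form were not available here. A question before dispensing, or an instruction to report a pregnancy, would sit naturally in H, I, Q or the consent form. This stands in full: the finding is that no re-check is stated in the available text, not that none exists.

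Second, the wording already gives a counselor grounds to withhold. Section 3.5.1 says such a person cannot receive NRT, and Section 4.6.3 makes participants eligible for NRT without requiring that everyone be given it. That is fair, but it helps only once the counselor knows. What is missing is the asking.

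Third, session 1 is in person and covers NRT risks, so a pregnancy may well come up. That is likely to reduce the number affected. However, the protocol did not rely on volunteered disclosure at entry, and it gives no reason to rely on it at supply.

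Fourth, the range of 0.3 to 3 people is 300 multiplied by a chosen number, and the documents do not quantify any harm. Both points are correct. The range shows scale and is not an estimate.

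**Conclusion.** The concern holds as a low-cost safety improvement to consider. Followed as written, the protocol could supply NRT to a control participant whom its own criterion says cannot have it, because the only stated check is about six months old. The number affected cannot be estimated from the documents and is probably very small. It falls below one expected person if fewer than 0.33% of the 300 controls are in this position at session 1 and accept NRT.

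The conclusion assumes that no unseen appendix or consent form contains a re-check; the sponsor can settle that by looking. It does not extend to the Intervention Arm, and it leaves the estimates, error rates and 6-month comparison as they are.

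**What to change.** In Section 4.6.3, require the counselor to repeat the pregnancy/breastfeeding question at session 1 before handing over NRT. Handover is the right point because the product is already at the study office by then, and it is the last stated step at which supply can be stopped. The question is essential in the Waitlist Arm; ask it in both arms only for uniformity.

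State the consequence as well: anyone answering yes receives no study NRT, but keeps counseling and follow-up and remains in the analysis as randomized.

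The question may also be added to the control-arm scheduling call (Appendix I). Since that call can come up to about three weeks before session 1, it cannot replace the question at handover.

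If Appendix F, H, I or Q or the consent form already contains a re-check, a cross-reference in Section 4.6.3 is enough.

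The cost is one question and one protocol sentence. The downside is that a few participants would not receive the NRT component.
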